### 7.2 Adverse Events

Treatment-emergent AEs (TEAEs) and non-TEAEs will be listed. TEAEs will be defined as AEs that occur on or after the date and time of study drug administration. Any AE that first occurs pre-dose but worsens in severity after the first study drug administration will also be considered a TEAE. Non-TEAEs are those that occur prior to the first administration of the study medication and resolved prior to dosing or that first occur prior to the first study drug administration but do not worsen in severity after dosing. TEAEs will be captured during the study until study exit. Adverse events will be followed-up until complete resolution, or until the Principal Investigator or Medical Sub-Investigator judges safe to discontinue follow-up.

The incidence of TEAEs will be summarized for each study part separately using the safety population. The MedDRA® dictionary Version 22.0 will be used to classify all TEAEs reported during the study by SOC and PT.

Incidence of subjects who experienced TEAEs will be presented by treatment, group and overall, SOC, PT, by Investigator-assessed relationship and also by severity. Each subject may only contribute once to each of the incidence rates, for a TEAE following a given treatment, regardless of the number of occurrences; the highest severity or highest relationship will be presented, as appropriate. In each table, SOC will be presented in descending order of overall incidence rate in terms of frequency of subjects and then in frequency of events (alphabetical order will be used in case of equal rates). For each SOC, PT will be presented the same way.

For each recorded AE or SAE, the Investigator or designee must make an assessment of intensity, if possible, based on the Common Terminology Criteria for Adverse Events (CTCAE) version 4.03 or later ([https://evs.nci.nih.gov/ftp1/CTCAE/CTCAE\\_4.03/CTCAE\\_4.03\\_2010-06-14\\_QuickReference\\_5x7.pdf](https://evs.nci.nih.gov/ftp1/CTCAE/CTCAE_4.03/CTCAE_4.03_2010-06-14_QuickReference_5x7.pdf)). A determination of grading at the time of AE occurrence is required in order to monitor for DLTs and may be modified upon continued assessment. If there is insufficient information to determine intensity, the AE must still be reported. The severity of an AE that cannot be termed and graded by the most current version of CTCAE will be categorized as follows (Table 4):

**Table 4: Classification of Adverse Event Intensity**

Grade 1	Mild; asymptomatic or mild symptoms; clinical or diagnostic observations only; intervention not indicated.
Grade 2	Moderate; minimal, local or noninvasive intervention indicated; limiting age-appropriate instrumental activities of daily living.
Grade 3	Severe or medically significant but not immediately life-threatening; hospitalization or prolongation of hospitalization indicated; disabling; limiting self-care activities of daily living.
Grade 4	Life-threatening consequences; urgent intervention indicated.
Grade 5	Death.

The relationship of TEAEs will be classified according to the study protocol as unrelated (not related), unlikely, possible, probable to nalbuphine.

The outcome of TEAEs will be classified according to the study protocol as fatal, resolved, resolved with sequelae and unresolved to nalbuphine.

Incidence of subjects who experienced TEAEs (frequency and the percentage of subjects) will be presented for each group and overall by:

- SOC and PT;
- SOC, PT, and relationship;

- SOC, PT, and maximum severity.

Number of TEAEs will also be presented by:

- SOC and PT;
- SOC, PT, and relationship;
- SOC, PT, and maximum severity.

Serious adverse events (SAEs) and TEAEs leading to early discontinuation of study drug will be listed separately.

### 7.3 Laboratory Parameters

For Part 1 of the study, clinical chemistry will be performed at screening, in the morning on Day -1, and on Day 4. For Part 2 of the study, clinical chemistry will be performed at screening, in the morning on Day -1, and on Days 5, 10, and 16. The following will be assessed: albumin, alkaline phosphatase, AST, ALT, urea, calcium, chloride, glucose, phosphorus, potassium, creatinine, sodium, bicarbonate (CO2), total bilirubin, indirect bilirubin, CPK, direct bilirubin, and total protein.

Considering that indirect bilirubin is calculated from total and direct bilirubin values, indirect bilirubin result would not be available in case of direct bilirubin below the limit of quantification.

Estimated glomerular filtration rate (eGFR) will be calculated by the MDRD4 Equation at screening.

For Part 1 of the study, hematology will be performed at screening, in the morning on Day -1, and on Day 4. For Part 2 of the study, hematology will be performed at screening, in the morning on Day -1, and on Days 5, 10, and 16. The following will be assessed: complete blood count with differential, hemoglobin, and hematocrit.

For Part 1 of the study, coagulation tests (PT, aPTT, and INR) will be performed at screening, in the morning on Day -1, and on Day 4. For Part 2 of the study, coagulation tests will be performed at screening, in the morning on Day -1, and on Day 16. The following will be assessed: prothrombin time/international normalized ratio (PT/INR) and activated partial thromboplastin time (aPTT).

For Part 1 of the study, urinalysis will be performed at screening, in the morning on Day -1, and on Day 4. For Part 2 of the study, urinalysis will be performed at screening, in the morning on Day -1, and on Day 16. The following will be assessed: macroscopic examination, pH, specific gravity, protein, glucose, ketones, bilirubin, occult blood, nitrite, urobilinogen, and leukocytes. Unless otherwise specified, microscopic examination will be performed on abnormal findings and these results will be listed only.

Listings of all clinical laboratory results (Clinical Chemistry, Hematology, Urinalysis and Coagulation) will be provided with the abnormal values flagged with "L" for low and "H" for high for continuous parameters, and "A" for abnormal for categorical parameters.

Descriptive statistics (mean, median, SD, Min, Max, and sample size) for each clinical laboratory test (continuous variables) will be presented by Cohorts and group for screening, check-in on Day -1 and study exit. Change from baseline descriptive statistics for study exit will be presented. Baseline will be defined as the last results (scheduled or unscheduled) obtained prior to the administration of nalbuphine. For categorical variables (urinalysis tests), the number of subjects (frequency and percentage) will be tabulated for each individual result (e.g., negative, positive, trace). Results from unscheduled or repeat tests will not be included in the summary statistics unless the repeat was required (and documented as such) due to technical reasons or an invalid initial result, or for baseline determination if applicable.

A summary table of shifts from baseline to study exit measurements will be provided. Baseline will be defined in the same manner as described in the preceding paragraph for continuous variables. The shift tables will include normal, low, and high relative to the laboratory reference ranges (or normal-abnormal for categorical variables). Results from repeat tests will not be included in the summary statistics unless the repeat was required (and documented as such) due to technical reasons or an invalid initial result.

If more than one clinical laboratory is used for the study, a formula that takes into consideration the relative normal ranges of each test of laboratories used will be applied in order to normalize these data. The conversion formula used will depend on the typical distribution of the normal range for each laboratory test; the two formulae used are presented below:

- Hemoglobin, hematocrit, and platelet count test results are considered to have a normal distribution ([Chuang-Stein, 1992](#)) and the following formula will be used ([Karvanen J., 2003](#)):

$$s = L_s + (x - L_x) \frac{U_s - L_s}{U_x - L_x}$$

- The remaining hematology, biochemistry, and urinalysis test results are considered to have a non-normal distribution ([Chuang-Stein, 1992](#)) and the following formula will be used ([Karvanen J., 2003](#)):

$$s = \frac{x U_s}{U_x}$$

U= upper limit; L= lower limit; s= primary facility result; and x= secondary facility results.

Prior to applying these formulae, if required, units will be adjusted.

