	
 Group 1: Child-Pugh Group A: score 5-6 points; 6-8 subjects with mild hepatic impairment Group 2: Child-Pugh Group B: score 7-9 points; 6-8 subjects with moderate hepatic impairment Group 3: Child-Pugh Group C: score 10-15 points; 4-6 subjects with severe hepatic impairment 
Cohort 5 (Part 1, SAD) will include dosing of healthy subjects with normal hepatic function (control group) to obtain 6-8 subjects who did not vomit within 6 hours of dosing or have any episode of vomiting in order to obtain adequate PK data.
 
The total number of subjects dosed (including potential replacement subjects) will remain within a maximum of 94 subjects for the whole study (up to 78 subjects in the SAD and up to 16 subjects in the MAD). Subjects enrolled in Cohort 1 can also be enrolled in Cohorts 2, 3, and 4. Subjects enrolled in Part 1 can also be enrolled in Part 2.
										
Screening Procedures:	
Demographic data, medical and medication histories, complete physical examination, body measurements, 12-lead electrocardiogram (ECG), vital signs (blood pressure, heart rate, and respiratory rate), pulse oximetry, body temperature, hematology, coagulation (PT, aPTT, and INR), clinical chemistry, human immunodeficiency virus (HIV), hepatitis B and C tests, urinalysis, WI--NRS (Part 2 only), urine and serum pregnancy test (females only), and urine alcohol and drug screen.
 
Assessment of liver function will be performed, and the degree of hepatic impairment will be categorized using Child-Pugh system at screening.
										
Confinement and Washout:	
Part 1 (SAD)
 
Subjects in Cohorts 1 to 4 will be confined from the morning of Day -1 until Day 4 (after the 72-hour post-dose blood draw).
 
Cohort 5 subjects will be confined from the morning of Day -1 until Day 3 (after the 48-hour post-dose blood draw). Subjects will come back to the clinic on Day 4 for the final blood draw and safety procedures at the study exit visit.
 
There will be a washout period of at least 7 days between each administration of the investigational product (IP) in Part 1 of the study and between Parts 1 and 2 of the study.
 
Part 2 (MAD)
 
Cohort 6 subjects will be confined from the morning of Day -1 until Day 16 (after the 72-hour post-last dose blood draw). Subjects will come back on Day 17 for the final blood draw (96-hour post-last dose blood draw) at the Study Exit visit.
										

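### SAP 7.3 leaves the Day 5 and Day 10 chemistry and hematology values, the only scheduled on-treatment draws in Part 2, out of the group-level laboratory tables

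*SAP*

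**What the plan says.** SAP 7.3 gives the Part 2 sampling days. For chemistry, "clinical chemistry will be performed at screening, in the morning on Day -1, and on Days 5, 10, and 16". For hematology, "hematology will be performed at screening, in the morning on Day -1, and on Days 5, 10, and 16". Coagulation has fewer draws: "coagulation tests will be performed at screening, in the morning on Day -1, and on Day 16". Urinalysis follows the same days as coagulation.

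The same section then names the outputs. Descriptive statistics for continuous tests "will be presented by Cohorts and group for screening, check-in on Day -1 and study exit". On change, "Change from baseline descriptive statistics for study exit will be presented". On shifts, "A summary table of shifts from baseline to study exit measurements will be provided". Nothing in the section treats Part 2 differently from Part 1.

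The protocol synopsis (Confinement and Washout) keeps Part 2 subjects in the clinic "until Day 16 (after the 72-hour post-last dose blood draw"). It adds: "Subjects will come back on Day 17 for the final blood draw (96-hour post-last dose blood draw) at the Study Exit visit". Protocol 9.11 places the Part 2 closing laboratory tests on Day 16 and only a PK sample on Day 17.

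Three other places bear on the point:
- The opening of SAP Section 7 says that laboratory values, like adverse events, vital signs and ECGs, will be summarised according to when they were collected, as appropriate.
- SAP 7.4 (vital signs) and 7.6 (ECG) summarise each time point and give change from baseline at all post-dose time points.
- SAP 2.1 makes safety and tolerability in hepatic-impaired subjects a primary objective.

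**The concern.** The list of output time points fits Part 1, where each dose level has one post-dose laboratory draw, on Day 4. It does not fit Part 2, where two chemistry and hematology draws fall within the titration and the third comes after dosing has stopped. Taken as written, the Part 2 tables would compare a pre-dose value with an off-treatment value and would show nothing from the dosing period.

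At stake is the group-level description of chemistry and hematology during dosing, by impairment class. Subjects in these groups may enter with abnormal liver tests, so a modest change in a group is easier to see in a change-from-baseline or shift table than in individual listings.

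**Working it through.** No power, alpha or sample-size figure is involved, and the documents give no figure to reproduce. The check compares scheduled days with tabulated days.

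**Inputs.** Sampling days and output time points come from SAP 7.3. Part 2 dosing runs from Day 1 to the morning of Day 13 (SAP Table 3-2). Day 16 is 72 hours after the last dose (protocol synopsis and 9.2).

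**Part 2 chemistry and hematology, scheduled against tabulated:**

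| Time point | Phase | Descriptive table | Change and shift tables |
|---|---|---|---|
| Screening | pre-dose | yes | only if it is the baseline value |
| Day -1 | pre-dose | yes | as baseline |
| Day 5 | on treatment | no | no |
| Day 10 | on treatment | no | no |
| Day 16 | 72 h after last dose | yes, if taken as study exit | yes, if taken as study exit |

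**Counts.**
- Descriptive table: 3 of 5 scheduled time points.
- Change-from-baseline and shift tables: 1 of 3 post-baseline time points, so 2 of 3 (67%) are omitted.
- On-treatment coverage: 0 of 2.
- With Part 2 at its maximum of 16 subjects (protocol 8.1), up to 16 × 2 = 32 subject-visits for each of chemistry and hematology are not tabulated.

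**Coagulation and urinalysis.** These have no Day 5 or Day 10 sample, so nothing is omitted.

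**General against specific text.** The Section 7 opening would cover Days 5 and 10, since they are collection time points. But its qualifier leaves the detail to the subsections, and 7.3 gives a definite list without them. The two statements do not agree, and the more specific one is the one that leaves the days out. The comparable subsections, 7.4 and 7.6, do follow the general rule.

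**What study exit means in Part 2.** The protocol schedule (4.2) calls Day 16 discharge and Day 17 study exit, and Day 17 has no laboratory tests. Read literally, the exit column would have no scheduled data. Read with protocol 9.11, it can only mean Day 16.

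**After the change.** Descriptive coverage becomes 5 of 5, change and shift coverage 3 of 3, and on-treatment coverage 2 of 2.

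**The case against.** The case for leaving the text alone has several parts.

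- **The values are not lost.** SAP 7.3 lists every laboratory result with low, high or abnormal flags, and with at most 8 subjects per impairment group a reader can follow each subject. This stands and limits the harm. A listing still does not summarise change by group.
- **Important abnormalities are tabulated elsewhere.** Protocol 9.15.3 records abnormalities judged clinically significant, including significant worsening of an abnormal baseline, as adverse events. SAP 7.2 tabulates those that are treatment-emergent. This also stands. A reader might infer that an on-treatment rise could escape every summary table. That holds only for changes the investigator does not judge clinically significant.
- **Intent is unclear.** The table shells are in a separate document, and the Section 7 opening points to fuller tables. The days may therefore have been overlooked rather than deliberately excluded, but the SAP text still needs reconciling.
- **No formal analysis depends on it.** A reader might infer that a primary safety analysis is compromised. The documents define none. Safety is a primary objective served by descriptive summaries. Dose-limiting toxicity is defined by graded adverse events and overnight oximetry (protocol 9.14), so those rules do not rest on these tables.

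A reader might also argue from the drug's half-life that Day 16 is too late to see a laboratory effect. At the Day 13 healthy-subject mean of 8.58 h (protocol Table 2), 72 / 8.58 = 8.4 half-lives have passed. That shows how far nalbuphine itself has cleared in healthy subjects, not how long a change in enzymes or bilirubin lasts, and the documents give no figure for the latter. Nor do they point to a liver signal: protocol 5.1.1.1 reports no chemistry or hematology changes attributable to nalbuphine in the toxicology studies and describes the most frequent adverse events as central nervous system and gastrointestinal.

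**Conclusion.** The point holds for Part 2 chemistry and hematology. SAP 7.3 states a rule that leaves both scheduled on-treatment draws out of the descriptive, change-from-baseline and shift tables. That rule conflicts with the Section 7 opening and differs from the handling of vital signs and ECG. The loss is confined to group-level on-treatment changes that are not reported as adverse events. The documents do not show that a particular signal would be missed.

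The conclusion assumes that the specific list in 7.3 governs over the general sentence and that study exit means Day 16. It applies only if Part 2 is conducted, since the study may end after Part 1. One limit remains after any correction: the 162 mg step starts on the evening of Day 10. If the Day 10 sample is drawn before that dose, the added columns will describe the earlier dose steps only.

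This is worth correcting because the data are already being collected. It does not threaten the study's conclusions.

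**What to change.** In SAP 7.3:

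1. For Part 2 chemistry and hematology, name Days 5 and 10 in the descriptive, change-from-baseline and shift tables, by group.
2. State that the Part 2 study exit laboratory value is the Day 16 sample, 72 hours after the last dose, and label it post-treatment.
3. Bring the wording into line with the opening of Section 7, and check that the table shells match.

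A shift from baseline to the worst on-treatment value is optional. With two scheduled draws it adds little to the two visit columns. Coagulation and urinalysis need no new time points.

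The cost is a few extra table columns and a short SAP edit, with no new samples and no change to study conduct.

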- 11) History of significant drug abuse (by subject report) within 1 year prior to screening. Use of soft drugs (such as marijuana) within 3 months prior to the screening visit. Hard drugs (such as cocaine, phencyclidine [PCP], crack, opioid derivatives including heroin, and amphetamine derivatives) use within 1 year prior to screening.
- 12) Participation in a clinical research study involving the administration of an investigational or marketed drug or device within 30 days prior to the dosing, administration of a biological product in the context of a clinical research study within 60 days prior to the dosing, or concomitant participation in an investigational study involving no drug or device administration.
- 13) Subjects using medication other than topical products without significant systemic absorption:
 - a) Prescription medication, including any mu-opioid agonist within 14 days prior to the administration of the IP;
 - b) Over-the-counter products and natural health products (including herbal remedies, homeopathic and traditional medicines, probiotics, food supplements such as vitamins, minerals, amino acids, essential fatty acids, and protein supplements used in sports) within 7 days prior to the first dosing, with the exception of the occasional use of acetaminophen (up to 2 g daily);
 - c) A depot injection or an implant of any drug within 3 months prior to the first dosing.
- 14) Subjects using any drugs known to induce or inhibit hepatic drug metabolism, including St. John's wort, within 30 days prior to IP administration.
- 15) Subject with a history of allergic reactions to nalbuphine, opioids, or other related drugs.
- 16) Subject has a history of anaphylaxis, a documented hypersensitivity reaction, or a clinically significant reaction to any drug.

- 17) Donation of plasma within 7 days prior to dosing. Donation or loss of blood (excluding volume drawn at screening or menses) of 50 mL to 499 mL of blood within 30 days, or more than 499 mL within 56 days prior to the dosing.
- 18) Hemoglobin < 12.8 g/dL (males) and < 11.5 g/dL (females) and hematocrit < 36% (males) and < 32% (females) at screening.
- 19) Lactating subject.
- 20) Inability or difficulty swallowing tablets.
- 21) Poor venous access or inability to tolerate catheter venous access.

9. Clinical Procedures

The study will be conducted jointly at inVentiv and the Orlando Clinical Research Center.

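### If more than one laboratory is used, the SAP's conversion for most laboratory tests aligns only the upper reference limit, so low-end values of two-sided tests such as albumin are shifted in the descriptive safety tables

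*SAP*

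**What the plan says.** The conversion is conditional: "If more than one clinical laboratory is used for the study", results from a secondary facility are put on the primary facility's scale (SAP 7.3). The documents do not say how many laboratories there are. The protocol names two sites: "The study will be conducted jointly at inVentiv and the Orlando Clinical Research Center" (section 9, Clinical Procedures).

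SAP 7.3 picks one of two formulas by the assumed distribution of the test and cites two methods papers:

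- "Hemoglobin, hematocrit, and platelet count test results are considered to have a normal distribution". These three use s = Ls + (x − Lx)(Us − Ls)/(Ux − Lx).
- "The remaining hematology, biochemistry, and urinalysis test results are considered to have a non-normal distribution". These use s = x·Us/Ux.

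The symbols are defined as "U= upper limit; L= lower limit; s= primary facility result; and x= secondary facility results".

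Clinical chemistry falls in the second group. Its list begins: "The following will be assessed: albumin, alkaline phosphatase, AST, ALT, urea, calcium, chloride, glucose, phosphorus, potassium, creatinine, sodium", and goes on to bicarbonate, bilirubin, CPK and total protein. Coagulation (PT, aPTT, INR) is collected and listed but is named under neither formula.

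The same section plans descriptive statistics by cohort and group, change from baseline to exit, and a shift table: "The shift tables will include normal, low, and high relative to the laboratory reference ranges". It does not say whether that table uses converted values against the primary range or original values against each laboratory's own range.

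**The concern.** A conversion meant to put two laboratories on one scale should carry a result at one laboratory's limit to the same limit at the other. The first formula does this at both ends. The second contains no lower limit. That is adequate for tests read only against an upper limit, such as ALT, AST, bilirubin or CPK. It is not adequate for albumin, total protein, sodium, potassium, calcium, chloride or bicarbonate, where a low value has its own meaning.

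Albumin is the clearest case. Child-Pugh scoring in Protocol 5.2.5 cuts it at 3.5 and 2.8 g/dL, so low albumin is part of what defines the impaired groups, and many of their results should lie where the conversion is not aligned. Safety and tolerability in impaired subjects is a primary objective, and these tables are part of how it is reported.

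**Working it through.** **Inputs.** The formulas and the assignment of tests come from SAP 7.3. The SAP states no figure on this point, so there is none to reproduce. The documents give no reference ranges, means or SDs. All of those below are assumptions: albumin in g/dL with mean 3.5 and SD 0.5; potassium in mmol/L with mean 4.1 and SD 0.45.

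**Step 1: what each formula does at the limits.**

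- Two-limit formula: x = Lx gives Ls, and x = Ux gives Us, for any pair of ranges. Class is always kept.
- Upper-limit formula: x = Ux gives Us, but x = Lx gives Lx·Us/Ux. This equals Ls only if Lx/Ux = Ls/Us (or both lower limits are zero).

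Under the upper-limit formula, the original value that lands on the primary lower limit is Ls·Ux/Us. Original values between Lx and Ls·Ux/Us change low/normal class if the converted value is read against the primary range. High/normal class never changes.

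**Step 2: assumed cases.** The last column is the normal probability between Lx and Ls·Ux/Us.

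| Test | Secondary range | Primary range | Lx becomes | Original values that change class | Direction | Share of secondary-laboratory results |
|---|---|---|---|---|---|---|
| Albumin | 3.4–5.4 | 3.5–5.0 | 3.15 | 3.40 to 3.78 | normal to low | 29% |
| Albumin | 3.5–5.0 | 3.5–5.5 | 3.85 | 3.18 to 3.50 | low to normal | 24% |
| Albumin | 3.5–5.2 | 3.5–5.0 | 3.37 | 3.50 to 3.64 | normal to low | 11% |
| Albumin | 3.3–4.8 | 3.5–5.0 | 3.44 | 3.30 to 3.36 | normal to low | 5% |
| Albumin | 3.4–5.0 | 3.5–5.2 | 3.54 | 3.365 to 3.40 | low to normal | 3% |
| Albumin | 3.5–5.0 | 3.64–5.2 (proportional) | 3.64 | none | none | 0% |
| Potassium | 3.5–5.3 | 3.5–5.1 | 3.37 | 3.50 to 3.64 | normal to low | 6% |

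First row in full: 3.4 × 5.0/5.4 = 3.15. The cut-off is 3.5 × 5.4/5.0 = 3.78. The share is Φ((3.78 − 3.5)/0.5) − Φ((3.4 − 3.5)/0.5) = Φ(0.56) − Φ(−0.20) = 0.29.

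**Step 3: the descriptive tables.** These shift however class is set. In the first row, an albumin of 3.5 converts to 3.5 × 5.0/5.4 = 3.24. The two-limit formula gives 3.5 + (3.5 − 3.4)(5.0 − 3.5)/(5.4 − 3.4) = 3.575. The gap is 0.33 g/dL. Change from baseline is multiplied by 5.0/5.4 = 0.93.

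**Step 4: is a class change a false shift?** The shift table compares baseline with exit in the same subject. If one laboratory runs both samples, the conversion only moves the cut-off, here from 3.40 to 3.78. Treating the SD of 0.5 as the total SD, and assuming within-subject SDs of 0.10, 0.15 and 0.20, low/normal shifts in either direction occur in 8.8%, 13.3% and 17.9% of subjects at 3.40, and in 7.7%, 11.6% and 15.5% at 3.78. Shifts do not increase. Most affected subjects move from normal/normal to low/low.

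**The case against.** The strongest reply is that a chain of conditions must hold. There must be more than one laboratory, and the protocol names two sites, not two laboratories. The ranges must not be proportional. For class to change, the shift table must read converted values against the primary range. The shift-table sentence in SAP 7.3 comes before the conversion paragraph and can naturally be read as each result against its own laboratory's range. All of this stands, and it limits the point to a conditional one. It does not remove it: the purpose of converting is to pool laboratories in the summaries, so the by-cohort and by-group statistics carry the shift on either reading.

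The SAP also bases its choice on the distribution of each test and cites published methods, which cannot be checked from these documents. Distribution is a fair reason to avoid a linear map for skewed tests. With assumed eosinophil ranges of 0.05–0.50 (secondary) and 0.02–0.50 (primary), the two-limit formula sends 0.01 to 0.02 + (0.01 − 0.05)(0.48/0.45) = −0.023. So the remedy cannot be the two-limit formula for every test with a lower limit. But whatever the distribution, s = x·Us/Ux still leaves the lower limit unaligned.

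Four stronger readings are tempting, and the documents do not support them:

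- That the shift tables will be wrong. The SAP leaves open which value and range they use.
- That 29% is a rate of false shifts. Step 4 shows otherwise.
- That site differences will appear as group differences. That needs groups to be spread unevenly across laboratories, and the documents do not describe the spread.
- That every test but three is affected. Coagulation is assigned neither formula, and the SAP tabulates urinalysis as categorical.

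**Conclusion.** The point holds in conditional form. If more than one laboratory is used and the ranges are not proportional, the stated rule shifts the low end of two-sided tests in either direction, and the descriptive laboratory tables carry that shift. If converted values are also classed against the primary range, about 3% to 29% of secondary-laboratory albumin results would change class in the non-proportional cases worked above, and none with proportional ranges. Those figures rest wholly on assumed ranges, mean and SD; the real size cannot be known from the documents.

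The reach is limited. Safety summaries are descriptive only (Protocol 12.3, SAP 7). Nothing in the documents makes adverse-event grading, Child-Pugh class or any PK result depend on converted values. The change is still worth making, because the formula is a stated rule and the correction costs very little.

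**What to change.** In SAP 7.3:

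1. Apply the existing two-limit formula to a named list of two-sided, roughly symmetric tests: the three already there plus, for example, albumin, total protein, sodium, potassium, calcium, chloride and bicarbonate. Keep s = x·Us/Ux for skewed tests and tests read only against an upper limit, such as ALT, AST, bilirubin, CPK and white-cell differentials.
2. State that low/normal/high in listings and shift tables is set from the original value against the reporting laboratory's own range. This removes class changes whatever the ranges are.
3. Assign PT, aPTT and INR a rule.

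The cost is a few sentences and a per-test formula flag in the programs, with no new data. If a single laboratory serves both sites, saying so would make the conversion rules unnecessary.
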